15.1 Serious Adverse Event (SAE) Reporting

An adverse event is considered serious if it results in ANY of the following outcomes:

- Death
- A life-threatening adverse event
- An adverse event that results in inpatient hospitalization or prolongation of existing hospitalization
- A persistent or significant incapacity or substantial disruption of the ability to conduct normal life functions
- A congenital anomaly/birth defect
- Important Medical Events (IME) that may not result in death, be life threatening, or require hospitalization may be considered serious when, based upon medical judgment, they may jeopardize the patient or participant and may require medical or surgical intervention to prevent one of the outcomes listed in this definition
- *List any additional events that require SAE reporting (pregnancy, AEs of special interest (AESI), secondary malignancies, etc.)*

Note: Hospital admission for a planned procedure/disease treatment is not considered an SAE.

SAE reporting is required as soon as the participant starts investigational treatment/intervention. SAE reporting is required for 30-days after the participant's last investigational treatment/intervention. Any event that occurs after the 30-day period that is unexpected and at least possibly related to protocol treatment must be reported.

Please note: Any SAE that occurs prior to the start of investigational treatment/intervention and is related to a screening test or procedure (i.e., a screening biopsy) must be reported.

Memorial Sloan Kettering Cancer Center
[name]
[name]

All SAEs must be submitted in PIMS. If an SAE requires submission to the HRPP office per [IRB SOP RR-408 'Reporting of Serious Adverse Events'](#), the SAE report must be submitted within 5 calendar days of the event. All other SAEs must be submitted within 30 calendar days of the event.

The report should contain the following information:

- The date the adverse event occurred
- The adverse event
- The grade of the event
- Relationship of the adverse event to the treatment(s)
- If the AE was expected
- Detailed text that includes the following
 - An explanation of how the AE was handled
 - A description of the participant's condition
 - Indication if the participant remains on the study
- If an amendment will need to be made to the protocol and/or consent form
- If the SAE is an Unanticipated Problem

15.2 External SAE Reporting

All SAEs/SUSARs (related and unrelated) will be recorded from the time of starting treatment until 30 days following the end-of-treatment exposure. Any SAEs/SUSAR considered possibly or probably related to the investigational product and discovered by the investigator at any time after the study should be reported.

All SAEs/SUSARs must be reported to SpringWorks within 5 business day of the first awareness of the event. MSK will provide a copy of the redacted MSK SAE report by fax or email to the assigned drug safety vendor below:

United BioSource Corporation
[name]
[name]
[contact]
[contact]

Additional follow-up information, if required or available, should all be reported to the assigned drug safety vendor within 5 business day of receipt. This should be completed on a follow-up MSK SAE form and faxed or emailed to the drug safety vendor with the original SAE/SUSAR information and kept with the appropriate section of the CRF and/or study file.

For IND/IDE protocols:

The SAE report should be completed as per above instructions. If appropriate, the report will be forwarded to the FDA by the IND Office.

Memorial Sloan Kettering Cancer Center
[name]
[name]

15.3 Dose Limiting Toxicities

The severity of adverse events (AEs) reviewed as potential dose-limiting toxicity (DLT) will be graded according to the CTCAE V.5.0. classification.

The occurrence of any of the following AEs during Cycle 1 (Day 1 – Day 28) will be considered a DLT, except for those AEs clearly related to disease progression or intercurrent illness.

Hematologic:

1. Grade 4 or greater hematologic toxicity (neutropenia, thrombocytopenia, or anemia)
2. Grade 3 febrile neutropenia (absolute neutrophil count [ANC] < 1000/mm³ with a single temperature of > 38.3°C (101°F) or a sustained temperature of ≥ 38°C (100.4°F) for > 1 hour)
3. Grade 3 thrombocytopenia with clinically significant bleeding

Non-hematologic:

1. Grade 2 or greater ocular toxicities leading to reduced visual acuity limiting ADL, glaucoma, retinal detachment, or retinal vascular disorder
2. NYHA class III or IV left ventricular dysfunction
3. Grade 3 or greater non-hematologic toxicity that is clinically significant with the following exceptions:
 - a. Toxicity (other than rash) that starts to resolve within 3 days of initiating optimal supportive care
 - b. Grade 3 rash that resolves to grade 1 or less within 7 days of initiating optimal supportive care
 - c. Grade 3 laboratory abnormalities that are not associated with clinical sequelae (e.g., isolated lactate dehydrogenase elevation) and resolves to Grade ≤1 within 3 days of initiating optimal supportive care
 - d. Grade 3 or 4 electrolyte laboratory abnormalities that last up to 72 hours, are not clinically complicated, and resolve spontaneously or respond to conventional medical interventions
 - e. Grade 3 or 4 amylase or lipase elevation that is not associated with symptoms or clinical manifestations of pancreatitis
 - f. Alopecia
4. Grade 4 non-hematologic toxicity, with the exception of those listed above, regardless of clinical significance or duration
5. Hy's law criteria (Grade ≥ 2 bilirubin in conjunction with grade ≥2 transaminase and without elevation of alkaline phosphatase)

In addition, clinically important or persistent toxicities not included above may also be considered a DLT at the discretion of the investigator after consultation with the SpringWorks physician.

A DLT may require temporary interruption or permanent discontinuation of mirdametinib. Mirdametinib treatment may be restarted at the same or reduced dose after the DLT has resolved to Grade ≤ 1 . See the mirdametinib treatment modification guidelines in Table 4 below.

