At each step of the 3+3 design, the investigators will review all available safety and PK data in the current Dose Level and decide about the appropriate next step. The subjects will become evaluable for the 3+3 decisions if they complete Cycle 1 and receive at least 80% of assigned drug doses, or if they exhibit a DLT in Cycle 1.

The starting dose of mirdametinib as single agent in each Dose Level escalation will be as follows:

- Dose Level 1: **mirdametinib 4 mg BID PO**, given continuously
- Dose Level 2: **mirdametinib 6 mg BID PO**, given continuously
- Dose Level 3: **mirdametinib 8 mg BID PO**, given continuously
- The de-escalation (Dose Level -1) may evaluate **mirdametinib 3 mg BID** given continuously, and (Dose Level -1INT) may evaluate **mirdametinib 3 mg BID** given on a 3 weeks on, 1 week off schedule. These de-escalation Dose Levels will be evaluated at investigator's discretion after the higher dose of mirdametinib is not tolerated. The de-escalation Dose Levels will be started only if the benefit-risk ratio is acceptable at the investigator's opinion.

The 3+3 decisions in Part 1 of Arm 2 will be made as follows.

1. Dose Level 1 (**mirdametinib 4 mg BID PO** given continuously)
 - a. Up to 3 subjects will be treated with mirdametinib as single agent at the dose of **4 mg BID PO** given continuously.

Memorial Sloan Kettering Cancer Center
[name]
[name]

- b. If 1 of the first 3 evaluable subjects in Dose Level 1 exhibit a DLT in Cycle 1, then Dose Level 1 will be expanded (see #2 below)
- c. If 0 of the first 3 evaluable subjects in Dose Level 1 exhibit a DLT in Cycle 1, then the dose of mirdametinib as single agent will be escalated to Dose Level 2 (**6 mg BID** given continuously) (see #4 below)

2. Dose Level 1 expansion:

- a. A sufficient number of subjects will be treated with mirdametinib as single agent at the dose of **4 mg BID PO** given continuously to accrue 6 evaluable subjects.
- b. If ≤ 1 of 6 evaluable subjects in the starting Dose Level exhibit a DLT in Cycle 1, then the dose of mirdametinib as single agent will be escalated to Dose Level 2 (**6 mg BID** given continuously) (see #5 below).
- c. If ≥ 2 of the first 3 evaluable subjects or ≥ 2 of the 6 evaluable subjects in Dose Level 1 exhibit a DLT in Cycle 1, then the mirdametinib dose will be de-escalated (see #3 below).

3. Dose Level -1 (de-escalation Dose Level **3 mg BID PO** given continuously)

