- a. Up to 3 subjects will be treated with mirdametinib as a single agent at the dose of 3 mg BID PO in Dose Level -1
- b. If ≤ 1 of the first 3 evaluable subjects in Dose Level -1 exhibit a DLT in Cycle 1, then a sufficient number of subjects will be treated with **mirdametinib 3 mg BID PO** given continuously to accrue 6 evaluable subjects.
- c. If ≤ 1 of 6 evaluable subjects in Dose Level -1 exhibit a DLT in Cycle 1, then **mirdametinib 3 mg BID PO** given continuously will be declared as the recommended dose for Part 2 (RP2D).
- d. If ≥ 2 of the first 3 evaluable subjects or ≥ 2 of the 6 evaluable subjects in the de-escalation Dose Level exhibit a DLT in Cycle 1, then the Arm 2 will be further de-escalated (see #4 below).

4. Dose Level -1INT (de-escalation Dose Level **3 mg BID PO** on a 3 weeks on, 1 week off schedule)

- a. Up to 3 subjects will be treated with mirdametinib as a single agent at the dose of 3 mg BID PO intermittently in Dose Level -1INT
- b. If ≤ 1 of the first 3 evaluable subjects in Dose Level -1INT exhibit a DLT in Cycle 1, then a sufficient number of subjects will be treated with **mirdametinib 3 mg BID PO** intermittently to accrue 6 evaluable subjects.
- c. If ≤ 1 of 6 evaluable subjects in Dose Level -1INT exhibit a DLT in Cycle 1, then **mirdametinib 3 mg BID PO** intermittently will be declared as the recommended dose for Part 2 (RP2D).

- d. If ≥ 2 of the first 3 evaluable subjects or ≥ 2 of the 6 evaluable subjects in the de-escalation Dose Level exhibit a DLT in Cycle 1, then the Arm 2 will be discontinued. The reason for discontinuation of Arm 2 would be that **3 mg BID PO** intermittently is deemed to be the minimum dose required for sufficient clinical benefit from mirdametinib as single agent in the refractory advanced cancer.

5. Dose Level 2 (Dose Level escalation **6 mg BID PO** given continuously)

- a. Up to 3 subjects will be treated with mirdametinib as a single agent at the dose of **6 mg BID PO** given continuously in Dose Level 2
- b. If ≤ 1 of the first 3 evaluable subjects in Dose Level 2 exhibit a DLT in Cycle 1, then a sufficient number of subjects will be treated with mirdametinib **6 mg BID PO** given continuously to accrue 6 evaluable subjects.
- c. If ≤ 1 of 6 evaluable subjects in Dose Level 2 exhibit a DLT in Cycle 1, then the dose of mirdametinib as single agent will be escalated to Dose Level 3 (**8 mg BID** given continuously) (see #6 below).

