- d. If ≥ 2 of the first 3 evaluable subjects or ≥ 2 of the 6 evaluable subjects in Dose Level 2 exhibit a DLT in Cycle 1, then **mirdametinib 4 mg BID PO** given continuously will be declared as the recommended dose for Part 2 (RP2D).

6. Dose Level 3 (Dose Level escalation **8 mg BID PO** given continuously)

- a. Up to 3 subjects will be treated with mirdametinib as a single agent at the dose of **8 mg BID PO** in Dose Level 3
- b. If ≤ 1 of the first 3 evaluable subjects in Dose Level 3 exhibit a DLT in Cycle 1, then a sufficient number of subjects will be treated with mirdametinib **8 mg BID PO** given continuously to accrue 6 evaluable subjects.
- c. If ≤ 1 of 6 evaluable subjects in Dose Level 3 exhibit a DLT in Cycle 1, then **mirdametinib 8 mg BID PO** given continuously will be declared as the recommended dose for Part 2 (RP2D).
- d. If ≥ 2 of the first 3 evaluable subjects or ≥ 2 of the 6 evaluable subjects in Dose Level 3 exhibit a DLT in Cycle 1, then **mirdametinib 6 mg BID PO** given continuously will be declared as the recommended dose for Part 2 (RP2D).
- e. The dose of mirdametinib as single agent will not be escalated above **8 mg BID PO** given continuously.

Arm 2 – Part 2 (expansion cohorts for mirdametinib as single agent)

One or more expansion cohorts (up to 30 subjects each) will be started, either in parallel or sequentially depending on the results of Part 1. The purpose will be to evaluate the efficacy and safety of the RP2D of mirdametinib as single agent (as determined in Part 1 of Arm 2) in the subjects with advanced solid cancers (with the exception of colorectal, small bowel, biliary and ampullary cancers) harboring activating mutations in MEK1/2.

Memorial Sloan Kettering Cancer Center
[name]
[name]

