13.3 Evaluable subjects

Patients who achieve sufficient compliance with the study drug intake in Cycle 1 (received at least 45 of 56 [greater than 80%] doses of mirdametinib (in Arm 1 only, also both doses of fulvestrant) **or** experience a DLT will be considered as evaluable for the assessment of the DLT rate for the particular dose level.

Additional patients should be enrolled at the same dose level as necessary to ensure an adequate number of DLT-evaluable patients.

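### The DLT rule in section 15.3 can be read to exempt Grade 4 non-hematologic events that begin to improve within 3 days, because exception 3a names no grade and item 4 imports it

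*Combined protocol and SAP*

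**What the plan says.** In section 15.3, non-hematologic item 3 makes clinically significant toxicity of Grade 3 or above a DLT, subject to exceptions a to f:

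- 3a: "Toxicity (other than rash) that starts to resolve within 3 days of initiating optimal supportive care". No grade is named.
- 3b: rash, limited to Grade 3.
- 3c: "Grade 3 laboratory abnormalities that are not associated with clinical sequelae", which must also return to Grade 1 or below within 3 days.
- 3d and 3e: certain electrolyte abnormalities and amylase or lipase rises, each naming Grade 3 or 4.
- 3f: alopecia.

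Item 4 then adds "Grade 4 non-hematologic toxicity, with the exception of those listed above, regardless of clinical significance or duration". A closing paragraph says that "clinically important or persistent toxicities not included above may also be considered a DLT at the discretion of the investigator", after consultation with the manufacturer's physician.

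Section 4.2 refers to section 15.3 for the DLT definition and builds the 3+3 rules on the count. In Arm 2, for example, escalation from 6 mg BID depends on the condition "If ≤ 1 of 6 evaluable subjects in Dose Level 2 exhibit a DLT in Cycle 1", and acceptance of 8 mg BID on "If ≤ 1 of 6 evaluable subjects in Dose Level 3 exhibit a DLT in Cycle 1". Section 13.3 treats a patient without a DLT as evaluable only if she or he "received at least 45 of 56 [greater than 80%] doses of mirdametinib" in Cycle 1 (in Arm 1, also both fulvestrant doses). It calls for extra enrolment to make up the number of evaluable patients.

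**The concern.** Item 3 covers Grade 4 as well as Grade 3, so its exceptions can reach Grade 4 events. Exceptions b to e state their grades; 3a does not. Item 4 excepts everything listed above it without limit. Taken literally, 3a therefore removes from the DLT count a Grade 4 non-rash event whose improvement has merely begun within 3 days of supportive care. Item 4's last words point the other way, since they say that neither clinical significance nor duration matters. Two investigators could score the same event differently.

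Section 15.0 defines Grade 4 as life-threatening. Section 4.2 acknowledges a wide gap in safety information on continuous dosing between the 2 mg/m² and 10 mg/m² levels, and Arm 2 escalates to 6 and 8 mg BID on a count in which a single event can decide the outcome. The patient may also drop out of the denominator as non-evaluable and be replaced.

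**Working it through.** **1. Which events depend on the reading.**

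| Event in Cycle 1 | 3a carried into item 4 | Only 3d–3f carried |
|---|---|---|
| Grade 4 hematologic | DLT | DLT |
| Grade 4 rash (outside 3a; 3b stops at Grade 3) | DLT | DLT |
| Listed ocular events, NYHA III/IV, Hy's law (own items) | DLT | DLT |
| Other Grade 4 non-hematologic, improving within 3 days (e.g. isolated AST/ALT, CK, neurologic, GI) | not a DLT | DLT |

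Only the last row is affected; 3d to 3f are exempt on both readings. Section 4.2 supplies no competing definition.

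**2. Evaluability.** Table 4 in section 15.4 permanently stops mirdametinib for Grade 4 AST/ALT. At two doses a day, a patient stopped on or before Day 22 has had at most 2 × 22 = 44 doses, one short of 45. If 3a exempts the event, that patient is neither a DLT nor evaluable, and is replaced.

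**3. The plan's own figures.** Section 14.1 tabulates escalation probabilities of 0.9, 0.7, 0.5, 0.3 and 0.2 at true DLT risks of 0.1 to 0.5. The standard 3+3 formula, (1−p)³ + 3p(1−p)²(1−p)³, gives 0.906, 0.709, 0.494, 0.309 and 0.172, which round to that table. Those figures are not in dispute.

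**4. Size of the effect.** Arm 1 Dose Level 1 and Arm 2 Dose Levels 2 and 3 expand to 6 unless at least 2 of the first 3 have a DLT, and pass with at most 1 DLT in 6:

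Pass(p) = (1−p)⁶ + 6p(1−p)⁵

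The documents give no rate q for the affected events. In section 3.2 the two studies nearest in dose report no Grade 4 events in 19 and 20 patients. For 0/39 the one-sided 95% upper bound is 1 − 0.05^(1/39) = 0.074. That bound covers all Grade 4 events over much longer than one cycle, but in plexiform neurofibroma, on an intermittent schedule, at no more than 4 mg BID. The affected set is narrower, so I assume q = 1%, 2% or 5%, on top of a base DLT risk of 20% or 10%. If the events count, p = base + q. If they are exempt and the patient stays evaluable, p = base. If they are exempt and the patient is replaced, p = base/(1−q).

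| Base 20% | q = 1% | q = 2% | q = 5% |
|---|---|---|---|
| Pass, exempt and evaluable | 0.655 | 0.655 | 0.655 |
| Pass, exempt and replaced | 0.650 | 0.645 | 0.630 |
| Pass, counted | 0.631 | 0.606 | 0.534 |
| Decision changes (evaluable) | 0.025 | 0.049 | 0.121 |
| Decision changes (replaced) | 0.020 | 0.039 | 0.096 |

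The last two rows are exempt minus counted. At base 10%, the pass probability is 0.886 if exempt (evaluable) and 0.866, 0.844 or 0.776 if counted. The chance that the question arises at all in a cohort of 6, 1 − (1−q)⁶, is 0.06, 0.11 or 0.26.

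**The case against.** The strongest reply is that the text has a sensible dominant reading. Exception 3a concerns time course, which item 4 declares irrelevant, whereas 3d to 3f name particular toxicities. Carrying over only the latter gives every phrase work to do. This is very likely the intent, but it is not written, and nothing elsewhere in the protocol supplies it.

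Second, 3c deals specifically with laboratory abnormalities and stops at Grade 3. Any abnormality meeting 3c has already begun to resolve, so letting 3a cover laboratory events leaves 3c nothing to do. It is also debatable whether an enzyme fall after stopping the drug is a response to supportive care. This weakens the AST/ALT example and the evaluability consequence drawn from it. It does not remove them, because the exceptions are alternatives, and it leaves neurologic and GI events untouched.

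Third, there are safeguards. The event stays in the AE data and is reported if it is an SAE. Sections 4.2 and 14.1 base the 3+3 on the overall safety profile as well as DLTs, and "the investigators will review all available safety and PK data in the current Dose Level" at each step. The DSMC oversees the trial, and one institution runs it. A Grade 4 event could also be declared a DLT under the closing paragraph. All of this stands and limits the harm. But that declaration is optional, and the counting rule is not corrected by it.

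Fourth, the event rates are assumed. That is so, and at 1% the effect is small.

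**Conclusion.** The concern holds. As written, section 15.3 allows a Grade 4 non-hematologic, non-rash event that starts to improve within 3 days to go uncounted, against the evident purpose of item 4. The event is not lost to safety reporting; what is uncertain is whether it enters the count and whether the patient enters the denominator. The affected set is narrow. With an assumed 20% base DLT risk, the reading decides an at-most-1-of-6 outcome about 2% of the time if 1% of patients have such an event, 4% to 5% at 2%, and 10% to 12% at 5%. These figures assume that investigators apply 3a literally and do not use their discretion. The effect is probably modest, but counting Grade 4 events towards a primary safety endpoint should not rest on discretion, so the wording should be corrected.

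**What to change.** Make two wording changes in section 15.3:

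1. Open exception 3a with *Grade 3*, so that it no longer reaches Grade 4.
2. In item 4, replace the general reference to the exceptions with *except as listed in 3d, 3e and 3f*, leaving the rest of the item unchanged.

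A Cycle 1 Grade 4 AST/ALT rise is then a DLT, so under section 13.3 the patient is evaluable and is not replaced.

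The cost is protocol wording only, with no added patients or visits. Slightly more events count as DLTs, so a dose level is slightly less likely to pass.

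Two neighbouring matters remain. Exception 3a would still overlap 3c for Grade 3 laboratory events. The evaluability gap also persists for exempt Grade 3 events: Table 4 interrupts drug for Grade 3 AST/ALT, and a 6-day interruption (12 missed doses) leaves 56 − 12 = 44, below 45. That needs its own evaluability rule.

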15.4 Dose Modification

The Investigator may temporarily interrupt, reduce the dose or permanently discontinue one or more study drugs at their discretion due to treatment-emergent adverse event that – in the Investigator's opinion – warrants treatment modification.

The treatment with fulvestrant in Arm 1 should be modified according to the USPI (where applicable) or at the investigator's discretion.

The treatment with mirdametinib in all arms should be modified according to the guidelines provided in Table 4 and Table 5 below.

Treatment should remain interrupted until the AE has resolved to Grade ≤ 1 (of Grade ≤ 2 in the event of rash). In addition, the AE resolution to Grade 2 may be acceptable at the Investigator's discretion if same toxicity was ongoing at Grade 2 since the pre-treatment baseline). The study treatment may be re-started at the same or lower dose (see Table 4 and Table 5) if the has reached satisfactory resolution in ≤ 21 days. If the AE has taken >21 to reach satisfactory resolution, then the study treatment should be permanently discontinued, unless the Investigator has determined that re-starting the treatment has acceptable benefit-risk ratio (e.g. continued objective response or stable disease after AE resolution).

Once a dose of the study treatment has been reduced due to an AE, the subject must remain on the reduced dose for the duration of the study. One subject may have up to 2 dose reductions due to AE. Dose re-escalation after the AE resolution is not permitted.

Table 4 Guideline for Mirdametinib Dose Modification for Related Adverse Events

RELATED ADVERSE EVENTS (Worst Grade by CTCAE V. 5.0)	INTERVENTION
NEUTROPENIA (ANC DECREASE)	
Grade 3 (ANC <1.0x to 0.5x 10 ⁹ /L)	Interrupt mirdametinib until resolution to Grade ≤1, then 
 • If resolved in ≤7 days, may re-start mirdametinib at the same dose at the Investigator's discretion • If resolved in >7 days, re-start mirdametinib at the next lower dose (see Table 5).
Grade 4 (ANC <0.5x 10 ⁹ /L)	Interrupt mirdametinib until resolution to Grade ≤1, then 
 • If resolved in ≤7 days, may re-start mirdametinib at the next lower dose (see Table 5) at the Investigator's discretion • If resolved in >7 days, permanently discontinue mirdametinib.
Grade 3 febrile neutropenia (ANC <1.0x 10 ⁹ /L with a single temperature of >38.3 degrees C [101 degrees F] or a sustained temperature of ≥38 degrees C [100.4 degrees F] for more than one hour)	Interrupt mirdametinib until complete resolution of fever and ANC resolution to Grade ≤1. After satisfactory resolution, re-start mirdametinib at the next lower dose (see Table 5).
Grade 4 febrile neutropenia (ANC and temperature criteria as listed above PLUS life-threatening signs or symptoms including septic shock, hypotension and/or acidosis)	Permanently discontinue mirdametinib.
THROMBOCYTOPENIA (PLATELET COUNT DECREASE)	
Grade 3 thrombocytopenia (Platelets <50x to ≥25x 10 ⁹ /L)	Interrupt mirdametinib until resolution to Grade ≤1, then 
 • If resolved in ≤7 days, may re-start mirdametinib at the same dose at the Investigator's discretion • If resolved in >7 days, re-start mirdametinib at the next lower dose (see Table 5).
Grade 4 thrombocytopenia (Platelets <25x 10 ⁹ /L)	Interrupt mirdametinib until resolution to Grade ≤1, then 
 • If resolved in ≤7 days, may re-start mirdametinib at the next lower dose (see Table 5) at the Investigator's discretion • If resolved in >7 days, permanently discontinue mirdametinib.
OPHTHALMOLOGICAL	

Any Grade \leq 2 event not leading to reduced visual acuity limiting ADL.	Continue mirdametinib at the same dose. Perform ophthalmologic exams at least monthly or more frequently at the Investigator's discretion until resolution to Grade \leq 1.
Any Grade 2 event reduced visual acuity limiting ADL, or any Grade \geq 3 event.	For events different from RVO or retinal detachment, interrupt mirdametinib until resolution to Grade \leq 1. Perform ophthalmologic exams at least biweekly or more frequently at the Investigator's discretion until satisfactory resolution. After resolution to Grade \leq 1, re-start mirdametinib treatment at the next lower dose (see Table 5). For Grade \geq 3 RVO or retinal detachment, permanently discontinue mirdametinib.
NEUROLOGICAL	
Grade \leq 2 seizure / convulsion, hallucination, confusion or delirium or similar events lasting >24 hours AND after ruling out other possible causes.	Interrupt mirdametinib until resolution to Grade \leq 1. After resolution to Grade \leq 1, re-start mirdametinib at the next lower dose (see Table 5).
Any Grade \geq 3 event	Interrupt mirdametinib until resolution to Grade \leq 1. After resolution to Grade \leq 1, the Investigator may re-start mirdametinib at the next lower dose (see Table 5) or permanently discontinue mirdametinib, depending on the Investigator's benefit-risk assessment.
MUSCULOSKELETAL	
Grade \geq 3 muscle weakness (symptomatic and interfering with ADL).	Interrupt mirdametinib until resolution to Grade \leq 1. After resolution to Grade \leq 1, re-start mirdametinib at the next lower dose (see Table 5).
DERMATOLOGICAL	
Grade \geq 3 rash	Interrupt mirdametinib until resolution to Grade \leq 1. After resolution to Grade \leq 1, re-start mirdametinib at the next lower dose (see Table 5).
LVEF	
Grade 2 LVEF decrease (post-baseline LVEF of 40-49%)	If asymptomatic, interrupt mirdametinib until LVEF resolves to \geq 50%. Perform LVEF exams at least biweekly or more frequently at the Investigator's discretion until satisfactory resolution. After resolution to Grade \leq 1, re-start mirdametinib at the next lower dose (see Table 5).

	If symptomatic, permanently discontinue mirdametinib.
Grade 3 LVEF decrease (post-baseline LVEF of 20-39% or $\geq 20\%$ difference between the post-baseline vs. baseline LVEF)	If asymptomatic, interrupt mirdametinib and repeat LVEF exam in one week. If repeat exam shows persistent Grade 3 LVEF decrease, then permanently discontinue mirdametinib. If repeat exam shows Grade 2 LVEF decrease or better, then apply the guideline listed above for Grade 2 LVEF decrease. If symptomatic, permanently discontinue mirdametinib.
Grade 4 LVEF decrease (post-baseline LVEF $< 20\%$)	Permanently discontinue study treatment.
QTcF	
Grade 3 QTcF prolongation (absolute QTcF > 500 msec or QTcF change from baseline > 60 msec)	Repeat ECG in triplicate approximately 1 hour after the initial ECG and consult with a cardiologist. The three ECGs must be recorded in close succession and not more than 2 minutes apart, and after at least 5 minutes of quiet supine rest. Calculate the mean QTcF from the three ECGs. If the absolute QTcF is < 480 msec or QTcF change from baseline is ≤ 30 msec on repeat ECG triplicate, and the cardiologist agrees, then mirdametinib may be re-started immediately at the same dose. If the absolute QTcF is > 480 msec to ≤ 500 msec or QTcF change from baseline is > 30 msec to ≤ 60 msec on repeat ECG triplicate, and the cardiologist confirms that the result is drug-related, then mirdametinib should be temporarily interrupted during the follow up by weekly repeat ECG triplicates. When the absolute QTcF is < 480 msec or QTcF change from baseline is ≤ 30 msec on repeat ECG triplicate, then mirdametinib should be re-started at the next lower dose (see Table 5). If the absolute QTcF is > 500 msec or QTcF change from baseline is > 60 msec on repeat ECG triplicate, and the cardiologist confirms that the result is drug-related, then mirdametinib should be permanently discontinued.
TOTAL BILIRUBIN	
Grade 2 total bilirubin increase ($> 1.5x$ to $3.0x$ ULN if baseline was normal; $> 1.5x$ to $3.0x$ baseline if baseline was abnormal)	Interrupt mirdametinib until resolution to baseline, then 
• If resolved in ≤ 7 days, re-start mirdametinib at the same dose• If resolved > 7 days, re-start mirdametinib at the next lower dose (see Table 5)
Grade 3 total bilirubin increase ($> 3.0x$ to $10.0x$ ULN if baseline was normal; $> 3.0x$ to $10.0x$ baseline if baseline was abnormal)	Interrupt mirdametinib until resolution to baseline, then 
• If resolved in ≤ 7 days, may re-start mirdametinib at the next lower dose (see Table 5) at the Investigator's discretion• If resolved > 7 days, permanently discontinue mirdametinib
Grade 4 total bilirubin increase ($> 10.0x$ ULN if baseline was normal; $> 10.0x$ baseline if baseline was abnormal)	Permanently discontinue mirdametinib

AST or ALT	
Grade 3 AST or ALT increase (>5.0x to 20.0x ULN if baseline was normal; >5.0x to 20.0x baseline if baseline was abnormal)	Interrupt mirdametinib until resolution to Grade ≤1 (or Grade ≤2 if the subject has liver metastases). After resolution to Grade ≤1, re-start mirdametinib at the next lower dose (see Table 5).
Grade 4 AST or ALT increase (>20.0x ULN if baseline was normal; >20.0x baseline if baseline was abnormal)	Permanently discontinue mirdametinib
Potential DILI / Hy's Law (pending clinical adjudication)	
Total bilirubin increase ≥2.0x ULN and ALT or AST increase ≥3.0x ULN	Permanently discontinue mirdametinib. If clinical adjudication confirms DILI / Hy's Law, then report DILI as SAE.
OTHER	
Grade ≥ 3 hematologic toxicities or clinically significant Grade 2 hematologic abnormalities that do not resolve within 72 hours after initiation of medical management.	Interrupt dosing, after resolution to Grade ≤ 1, restart study treatment at the next lower dose following Table 5.
Grade ≥ 3 nonhematologic toxicity that is not controlled by optimal supportive medication.	Interrupt dosing; after resolution to Grade ≤ 1 or baseline, restart study treatment at the next lower dose following Error! Reference source not found.
Other Grade 2 toxicity that is subjectively intolerable (except alopecia) and not controlled by optimal supportive medication.	Interrupt dosing; after resolution to Grade ≤ 1 or baseline, restart study treatment at the same dose.
Recurrent subjectively intolerable toxicity (at least a week interruption on 2 occasions) that is not controlled by optimal supportive medication.	Interrupt dosing; after resolution to Grade ≤ 1 or baseline, restart study treatment at the next lower dose using Error! Reference source not found. If toxicity is still intolerable, permanently discontinue study treatment (unless otherwise discussed with the Principal Investigator).

ADL=activities of daily living; LVEF=left ventricular ejection fraction

In the event a dose reduction is required, the study treatment total daily dose will be reduced as shown in Table 5:

Memorial Sloan Kettering Cancer Center
 [name]
 [name]

Table 5 Mirdametinib Dose Reduction

Dose at the time of the event	Reduced dose
2 mg BID	1 mg BID
4 mg BID	2 mg BID
6 mg BID	4 mg BID

BID = twice daily

